4.4 REASONS OFF TREATMENT

Patients will be taken off treatment if any of the following occur (off treatment assessments should be completed within 30 days \pm 2 days; please refer to Section 8.3):

- 1. Disease progression on treatment
- 2. Intolerable toxicity
- 3. Treatment (either one or both therapies) is interrupted for more than 3 weeks for any reason.
- 4. An intercurrent illness, which would in the judgment of the Investigator, affect assessments of clinical status to a significant degree or require discontinuation of study treatment
- 5. Non-protocol therapy (chemotherapy, radiotherapy, hormonal therapy, immunotherapy, or surgery) is administered during study treatment
- 6. Noncompliance with protocol or treatment
- 7. Becomes pregnant
- 8. Refuses to continue treatment (patient will continue to be followed for survival)
- 9. Completion of treatment portion of the protocol
- 10. Patients who achieve a confirmed clinical complete response
- 11. Physician decision

The date of and reason for discontinuation must be noted on the Change of Status page of the Case Report Form (CRF). Every effort should be made to complete the appropriate assessments.

4.5 REASONS OFF STUDY

Patients will be considered off study if any of the following occur:

- 1. Withdrawal of consent (patient will not be contacted and no further information will be collected). All data collected prior to withdrawal of consent may be used in the data analysis.
- 2. Termination of study by Baylor IRB, Eli Lilly and Company, or Principal Investigators
- 3. Lost to follow-up (3 attempts should be documented in the patient's source document before the site considers the patient as LFU)
- 4. Death

The date of and reason for discontinuation must be noted on the Case Report Form (CRF). Every effort should be made to complete the appropriate assessments.

If the patient is withdrawn for any reason, the end of study assessments must be completed. Patients who withdraw from the study treatment due to intolerable toxicity will still be followed for outcome and toxicity, per protocol.

Patients must still be followed for adverse events (AEs) for 30 calendar days after their last dose of study drug. All new AEs occurring during this period must be reported and followed until resolution, or after 30 days (whichever comes first), unless, in the opinion of the investigator, these values are not likely to improve because of the underlying disease. In this case, the

investigators must record his or her reasoning for this decision in the patients' medical records and as a comment on the CRF.

All patients who have CTCAE grade 3 or 4 laboratory abnormalities at the time of withdrawal must be followed until the laboratory values have returned to grade 1 or 2, or until 30 days after the date of withdrawal (whichever comes first), unless it is, in the opinion of the investigator, not likely that these values are to improve because of the underlying disease. In this case, the investigator must record his or her reasoning for making this decision in the patients' medical records and as a comment on the CRF.

5 CONCOMITANT THERAPY

Administration of other chemotherapy or immunotherapy, or hormonal therapy, or experimental medications during the study is not allowed. Patients cannot receive radiation therapy while receiving study therapy without previous discussion with the PI.

Supportive care such as granulocyte colony stimulating factor (G-CSF; filgrastim; pegfilgrastim or other biosimilars) may be administered at the discretion of the Investigator. Replacement steroids are permitted. All concomitant treatments, including blood and blood products, must be reported on the source documentation (not necessarily in the CRF). The following concomitant medications **must** be documented on the Con Meds page of the CRF:

- Blood and blood products
- Prophylactic antibiotics
- Premedications (ie, diphenhydramine)

- Antifungals
- Growth factors

No herbal therapies or alternative therapies will be permitted.

Bisphosphonates or denosumab will be allowed for treating osteoporosis or bone metastases.

5.1 DRUG-DRUG INTERACTIONS

5.1.1 LY3023414

Drugs causing QTc interval prolongations should be avoided for all patients in the study.

LY3023414 is a weak inhibitor of cytochrome P450 (CYP)3A4 Drugs that are either sensitive substrates of CYP3A4 or CYP3A4 substrates with a narrow therapeutic range should be administered with caution in combination with LY3023414. In addition, it is recommended to avoid strong inhibitors of CYP3A4 and strong and moderate inducers of CYP3A4 while receiving LY3023414.

Certain fruits, fruit juices and herbal supplements (grapefruit, star fruit, Seville oranges, pomegranate, gingko, goldenseal) may inhibit CYP3A4 isozyme, however, the degree of that inhibition is unknown.²⁶

A sample list of drugs that have known interaction with cytochrome P450 can be found here: http://medicine.iupui.edu/flockhart/table.htm.

5.1.2 Prexasertib

On days when prexasertib is administered, patients should avoid taking multiple (more than one) concomitant medications that are known or suspected to cause prolonged QTc or Torsades de Pointes and, if possible, alternative agents should be considered.²⁷

[figure not shown]
6 THERAPEUTIC AGENTS

6.1 LY3023414

LY3023414 is an investigational, orally available, potent selective inhibitor of the class I PI3K isoforms, mTOR, and DNA-PK. LY3023414 is being evaluated as a monotherapy and in combination with other agents in patients with advanced and/or metastatic solid tumors. Eli Lilly and Company is the manufacturer of LY3023414.²⁶

6.1.1 Formulation

LY3023414 is an inhibitor of the PI3K/mTOR pathway; the chemical name is 2H-Imidazo(4,5-c)quinolin-2-one, 8-(5-[1-hydroxy-1-methylethyl]-3-pyridinyl)-1-([2S]-2-methoxypropyl)-3-methyl. LY3023414 is a white to light yellow solid with the molecular formulation C₂₃H₂₆N₄O₃ and a molecular weight of 406.48. The chemical structure is below:²⁶

LY3023414

6.1.2 Storage and Stability

The drug product is packaged in bottles, which may contain desiccant, and is stable when stored at room temperature conditions according to the label. It is very slightly soluble in water, and slightly soluble in ethanol.²⁶

6.1.3 Preparation and Administration

The capsule drug product is composed of LY3023414 with no inactive ingredients, with the exception of the 200-mg capsules, which may also contain colloidal silicon dioxide.

The 10-mg capsules are opaque and orangish-red in color on the body and cap. The 25-mg capsules are opaque and white in color on the body and cap. The 100-mg capsules are opaque and blue in color on the body and cap. The 200-mg capsules are opaque and orangish-red in color on the body and cap.

The tablets are composed of LY3023414 and inactive ingredients such as microcrystalline cellulose, croscarmellose sodium, silicon dioxide, sodium stearyl fumarate, and a colorant.

The 50-mg tablets are green, modified, capsule-shaped tablets. The 100-mg tablets are dark yellow, modified, capsule-shaped tablets. The 150-mg tablets are green, modified, capsule-shaped tablets. The 200-mg tablets are light yellow, modified, capsule-shaped tablets.²⁶

6.1.4 Pharmacokinetics

Pharmacokinetic parameters of LY3023414 were evaluated in rats and dogs; data can be found in the prexasertib Investigator's Brochure.²⁶

In summary, LY3023414 exposures are generally similar in healthy subjects and cancer patients: in healthy subjects, LY3023414 plasma AUC $_{(0-\infty)}$ and C $_{max}$ are 2760 ng·hr/mL (CV 48%, n=20) and 777 ng/mL (CV 76%, n=20) and in cancer patients LY3023414 blood AUC $_{(0-\infty)}$ and C $_{max}$ are 2710 ng·hr/mL (CV 45%, n=37) and 828 ng/mL (CV 68%, n=54) following LY3023414 200 mg single administration. For further details, please refer to the LY3023414 Investigator's Brochure.²⁶

6.1.5 Adverse Effects

For LY3023414 monotherapy (N=108), the most common (that is, occurring in \geq 10% of patients) treatment-emergent adverse events (TEAEs) that were considered possibly related to LY3023414 in Study CBBA (N=96) included nausea (36.5%), fatigue (36.5%), vomiting (31.3%), decreased appetite (22.9%), diarrhea (20.8%), rash (13.5%), and oral mucositis (11.5%). Most of these TEAEs were graded as mild or moderate in severity.

LY3023414 monotherapy has been also studied in Asian cancer patients (a Japanese cancer population) in Study CBBH (N=12). The most common (that is, occurring in ≥5 patients) TEAEs that were considered possibly related to LY3023414 in this study included stomatitis (9 patients), nausea (8 patients), decreased appetite (7 patients), and platelet count decreased, anemia, and diarrhea (each 5 patients). Most of these TEAEs were graded as mild or moderate in severity.

The most frequently (that is, occurring in ≥4 patients) reported SAEs regardless of causality within the LY3023414 clinical program included dyspnea (10 patients), nausea and fatigue (each 5 patients), and dehydration, atrial fibrillation, abdominal pain, diarrhea, deep vein thrombosis, and hypotension (each 4 patients). Two deaths were considered due to SAEs (1 case each of pneumonia and pneumonia fungal) which were not related to study treatment. For further details, please refer to the LY3023414 Investigator's Brochure. ²⁶

Pregnancy

Animal reproduction studies have not been conducted with LY3023414. It is not known whether LY3023414 can affect reproductive capacity in humans. There is no clinical trial experience in pregnant individuals. However, based on data from an embryo–fetal developmental study, LY3023414 has the potential for teratogenicity and embryo/fetotoxicity and, therefore, may result in fetal harm when administered to a pregnant woman. LY3023414 must not be given to pregnant women. To minimize any potential risk, pregnant and breastfeeding women must be excluded from clinical trials of LY3023414. Women of childbearing potential should be advised to avoid becoming pregnant during therapy with LY3023414 and should be administered pregnancy tests prior to each cycle of treatment. Investigators should advise men to avoid

fathering a child during therapy with LY3023414. Both males and females with reproductive potential must agree to use medically approved contraceptive precautions during the study and for at least 3 months following the last dose of the study drug. Upon documentation of pregnancy, the patient must be removed from the study and treatment with study drug(s) must be stopped immediately.²⁶

Nursing Mothers

There are no available data on the effects of inhibition of PI3K and mTOR pathway on lactation. The potential effects of LY3023414 use during lactation are not known. Women who are breastfeeding should not take LY3023414.²⁶

Please see the Investigator's Brochure for additional adverse events and complete drug information.

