8.2 ASSESSMENTS DURING TREATMENT

The following assessments will be performed during therapy on Day 1 prior to the start of each cycle, unless otherwise specified. A Cycle is defined as 28 days (prexasertib dosing on Day 1 and 15).

There is a window (**up to 4 calendar days prior to the scheduled time point**) for assessments during the study. Any delay within this window is NOT a deviation. Assessments that are to be done on days when study drug is administered must be done **prior to dosing** as these assessments (CBC, CMP, assessment of response, etc) may determine whether or not drug is administered, or if a dose reduction is necessary, unless otherwise noted.

Note for Cycle 1 only: the prestudy assessments that correspond to assessments below may be used as Cycle 1 assessments as long as they are completed within the 72 hours prior to the patient receiving their first dose of study drug. If more than 72 hours have elapsed since the prestudy assessment, the assessment must be repeated for Cycle 1.

- 1. A brief medical history, to capture events that have occurred since the last cycle. Events that were not captured in the baseline complete medical history should be recorded on the AE page of the CRF.
- 2. A brief physical examination, including vital signs and body weight
- 3. ECOG PS (Appendix III)
- 4. Assessment of concomitant medications
- 5. A CBC with differential and platelet count on Day 1 and Day 15 of every cycle
- 6. A CMP Day 1 and Day 15 of each cycle
- 7. Assessment of magnesium (Mg) and phosphorus (P) Day 1 and Day 15 of each cycle
- 8. HbA1c must be obtained Day 1 and Day 15 of each cycle
- 9. Fasting serum glucose must be obtained Day 1 and Day 15 of each cycle
- 10. A pre-dose ECG (within 10 minutes of beginning prexasertib infusion) must be obtained on Cycle 1 and Cycle 2. Additional ECG may be obtained if clinically indicated.
- 11. A post-dose ECG (within 10 minutes of ending prexasertib infusion) must be obtained on Cycle 1 and Cycle 2. Additional ECG may be obtained if clinically indicated. **NOTE:** it is

- preferred to complete the post-dose ECG upon completion of the prexasertib infusion, but prior to LY3023414 dosing.
- 12. Tumor response by clinical assessment of the patient's disease (ie, by physical examination)

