12.3 PREGNANCY

Patients of child-bearing potential participating must agree to use one highly effective (less than 1% failure rate) method of contraception or use a combination of two effective methods of contraception during treatment with study drug and for at least 12 weeks following the last dose of study drug.

Note: Unless not allowed by local regulations, patients of child-bearing potential who are abstinent (if this is complete abstinence, as their preferred and usual lifestyle) or in a same sex relationship (as part of their preferred and usual lifestyle) must agree to either remain abstinent or stay in a same sex relationship. Periodic abstinence (eg, calendar, ovulation, symptothermal, postovulation methods), declaration of abstinence just for the duration of a trial, and withdrawal are not acceptable methods of contraception.

Women of child-bearing potential participating must test negative for pregnancy prior to initiation of treatment as indicated by a negative pregnancy test at the screening visit (prior to biopsy) and within 24 hours prior of drug exposure.

If pregnancy is confirmed in a patient during the course of the study, the patient must be taken off treatment and the pregnancy must immediately be recorded on the source documents and CRF, and will be reported by completing the Pregnancy Notification Form and emailing the form to the PI. Any pregnancy that occurs in a female partner of a male study participant will also be immediately recorded on the source documents and CRF and will be reported by completing the Pregnancy Notification Form and emailing the form to the PI. In addition, the Investigator must report to the Baylor IRB any follow-up information regarding the course of the pregnancy, including perinatal and neonatal outcome. Infants will be followed for a minimum of 8 weeks.

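### Section 6.1.5 asks for a pregnancy test before every LY3023414 cycle, but Section 8.2 and Appendix II schedule none between the first dose and the end-of-treatment visit

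*Combined protocol and SAP*

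**What the plan says.** Section 6.1.5, under Pregnancy, warns that "LY3023414 has the potential for teratogenicity and embryo/fetotoxicity" and bars its use in pregnant women. It then says that women of childbearing potential "should be administered pregnancy tests prior to each cycle of treatment". If a pregnancy is documented, "treatment with study drug(s) must be stopped immediately".

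The stopping rule is repeated in the operative sections. Section 4.4 lists "Becomes pregnant" as a reason to come off treatment, and Section 12.3 says: "If pregnancy is confirmed in a patient during the course of the study, the patient must be taken off treatment".

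Testing is placed as follows:

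- **Section 8.1, item 13:** a serum test in the 7 days before registration.
- **Section 12.3:** women of childbearing potential "must test negative for pregnancy prior to initiation of treatment as indicated by a negative pregnancy test", once at screening and again in the 24 hours before drug exposure.
- **Section 8.2:** opens with "The following assessments will be performed during therapy on Day 1 prior to the start of each cycle, unless otherwise specified" and lists 18 items. None is a pregnancy test.
- **Section 8.3, item 5:** a serum test at the off-treatment visit.
- **Appendix II:** the serum pregnancy test row has entries for prestudy and end of treatment. The during-treatment and follow-up cells are empty.

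**The concern.** The protocol gives a testing frequency in its drug-information section and a different one in the schedule that sites work from. Section 8 makes Appendix II the schedule of assessments and requires a deviation record when a required procedure is missed. A test with no slot in Section 8.2 or Appendix II is likely to be neither done nor noticed as missing.

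The rules that stop treatment on pregnancy protect only if the pregnancy is found. The one scheduled test after the first dose falls at the off-treatment visit, when dosing has already ended, so it cannot limit exposure. Treatment continues until progression or unacceptable toxicity, so the women who do best on the drugs have the longest untested period.

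**Working it through.** **Step 1. Count the scheduled tests.**

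| Period | Asked for in 6.1.5 | Scheduled | Where |
|---|---|---|---|
| Before first dose | 1 (before Cycle 1) | 2 | 8.1 item 13 and Appendix II (7 days before registration); 12.3 (screening, and 24 hours before exposure) |
| Cycle 2 onward, on treatment | 1 per cycle | 0 | not in 8.2, Appendix II or 12.3 |
| After treatment | not addressed | 1 | 8.3 item 5; Appendix II |

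The screening test in 12.3 is counted as the same test as that in 8.1.

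The empty during-treatment cell in Appendix II is not an artefact of text extraction, because Sections 8.1, 8.2 and 8.3 show the same pattern independently. The 24-hour test in Section 12.3 cannot be read as recurring: its sentence makes both tests conditions for starting treatment.

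**Step 2. Time on drug with no scheduled test after the first dose.**

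Inputs: a 28-day cycle (8.2); LY3023414 twice daily on Days 1 to 28 (7.2.2, Table 1); prexasertib on Days 1 and 15 (7.2). Assume no delays or dose reductions. For *n* cycles:

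- days on drug = 28*n*
- LY3023414 doses = 2 × 28*n*
- prexasertib infusions = 2*n*

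The protocol fixes no number of cycles, so *n* is assumed:

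- *n* = 2 takes a patient to the first 8-week scan (8.2, item 13).
- *n* = 6 follows if the 18-month maximum in Section 8.4 includes the 1-year follow-up. That leaves 6 months, about 183 days, and 183 / 28 = 6.5, so 6 full cycles.

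| | Days | LY3023414 doses | Prexasertib infusions |
|---|---|---|---|
| Current schedule, *n* = 2 | 56 | 112 | 4 |
| Current schedule, *n* = 6 | 168 | 336 | 12 |
| Day 1 test every cycle (longest gap) | 28 | 56 | 2 |

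**Step 3. Avoidable exposure.**

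Take a pregnancy that a test on Cycle 2 Day 1 would detect. If it is not noticed until treatment ends, the extra time on drug is 28(*n* − 1) days: 28 for *n* = 2 and 140 for *n* = 6. Both are maxima, because the pregnancy may be noticed clinically before then.

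**Step 4. Upper bound.**

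If treatment itself could fill the 18 months, that is 18 × 30.44 = 548 days. Then 548 / 28 = 19.6, which gives 20 cycle starts and 19 tests after Cycle 1 Day 1 that Section 6.1.5 asks for and the schedule omits.

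**The case against.** The strongest reply concerns the status of the sentence. It is a *should*, in a section that summarises the Investigator's Brochure. The items the same text makes mandatory (no use in pregnancy, contraception, stopping on pregnancy) are all in the operative sections. Section 6.1.5 is also protocol text, so staff who read the whole document are told to test.

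That bears on severity, but the mismatch remains. The protocol makes the recommendation, gives no reason to depart from it, and asks for testing alongside contraception rather than instead of it.

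A second reply is that the risk is small: 10 patients, required contraception, and possibly no women of childbearing potential. This is fair. The number is not given and could be anywhere from 0 to 10. A pregnancy might also come to light at the brief medical history in Section 8.2, item 1. That is a weak substitute, since Section 6.1.5 reports nausea (36.5%), fatigue (36.5%) and vomiting (31.3%) as common effects of LY3023414, and these could mask early pregnancy.

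Third, the exposure figures rest on assumed treatment lengths and no delays, while Section 7.2.3 allows delays of up to 3 weeks. This stands as a limit on their precision. The 6-cycle case is not an upper bound, as Step 4 shows.

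Fourth, the per-cycle recommendation is for LY3023414 only, so prexasertib infusions might seem irrelevant. They belong because the stopping rule in Section 6.1.5 covers the study drugs together.

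Finally, requiring a negative result goes further than asking for a test. It follows, however, from the bar on giving LY3023414 to pregnant women in the same paragraph.

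**Conclusion.** The concern holds. The schedule contains 0 pregnancy tests between the first dose and the end-of-treatment visit, where Section 6.1.5 asks for one before each cycle. That count needs no assumption. The consequence, 56 days on drug without a scheduled test for 2 cycles or 168 days for 6 against at most 28 with Day 1 testing, depends on the assumed number of cycles and on uninterrupted dosing. Any actual harm depends on a pregnancy occurring, and the protocol gives no basis for putting a probability on that.

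The change should be made on patient-safety grounds. It has no bearing on the sample size or the response-rate analysis. The exclusion, contraception and stopping provisions are properly placed and are not in question.

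**What to change.** Add an item to Section 8.2, and a matching entry in the during-treatment column of Appendix II, worded along these lines: *Pregnancy test for women of childbearing potential on Day 1 of each cycle, before dosing; a negative result is required before study drug is given.* State whether serum or urine is acceptable, so that waiting for a result does not hold up dosing. For Cycle 1, cross-refer to the 24-hour test in Section 12.3 and show that test in Appendix II as well, since it does not appear there or in Section 8.1.

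The running cost is one pregnancy test per cycle for each woman of childbearing potential. No extra visit is needed, because Section 8.2 already requires "A CBC with differential and platelet count on Day 1 and Day 15 of every cycle", together with a metabolic profile on the same days. As a change to study procedures it would need a formal amendment with IRB approval under Section 13.3.

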6.2 PREXASERTIB (LY2606368)

Prexasertib mesylate monohydrate (hereafter, and on the cover page, referred to as prexasertib) is an investigational, adenosine triphosphate—competitive selective inhibitor of checkpoint kinase 1 (CHK1). Prexasertib is being developed as a treatment for patients with advanced cancer and may have utility both as a single agent and in combination with other DNA-damaging agents or targeted agents. Eli Lilly and Company is the manufacturer of prexasertib.²⁷

6.2.1 Formulation

Prexasertib is an inhibitor of CHK1; the chemical name is 2-pyrazinecarbonitrile, 5-[[5-[2-(3-aminopropoxy)-6-methoxyphenyl]-1H-pyrazol-3-yl]amino] monomesylate monohydrate. Prexasertib is a yellow to white solid with the molecular formulation $C_{18}H_{19}N_7O_2\cdot CH_4O_3S\cdot H_2O$ and a molecular weight of 479.51. The chemical structure is below:²⁷

6.2.2 Storage and Stability

The drug product, prexasertib for injection, is supplied for clinical trial use as a lyophilized, yellow to white solid in glass vials and is composed of prexasertib mesylate monohydrate and the inactive ingredient sulfobutylether-β-cyclodextrin (Captisol). The drug product is available as either a 40 mg or 20 mg strength vial of the base compound prexasertib. The 40-mg strength vial

contains a 3% excess and the 20 mg strength contains a 5% excess to facilitate the withdrawal of the label amount for application with an appropriate device, such as an infusion set.

The drug product is stable when stored at room temperature. The reconstituted formulation is stable for at least 24 hours at room temperature; however, because the reconstituted drug product does not contain a preservative, the unused solution must be discarded after 12 hours.²⁷

